6.7 Definitions of Dose-Limiting Toxicity, Maximum Tolerated Dose, and Recommended Phase 2 Dose

6.7.1 DLT-Evaluable Criteria

The DLT evaluation period will be the first treatment cycle. Patients must have taken a minimum of 6 AR-42 doses **and** a minimum of 21 pazopanib doses during cycle 1 to be considered evaluable for DLT, if DLT has not been observed at the delivered dose.

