6.7.2 DLT Definition

DLT is defined as **any** ≥ **grade 3** toxicity occurring during the DLT evaluation period and attributed to one or both of the study medications **EXCEPT the following:**

- The first incidence of grade 3 PPE at any dose level (subsequent incidences of grade 3 PPE will be considered DLT)
- Grade 3 nausea and vomiting in the absence of adequate prophylaxis and/or responsive to medical management within 48 hours
- Grade 3 diarrhea in the absence of adequate prophylaxis and/or responsive to medical management within 48 hours
- Grade 3 fatigue responsive to medical management
- Grade 3 asymptomatic hypertension lasting \leq 7 days
- Grade 3 electrolyte abnormalities that are corrected within 48 hours and, when corrected, can be maintained
- Grade 3 asymptomatic lipase elevation lasting \leq 7 days
- Grade 3 decrease in platelet count if no clinically significant hemorrhage has occurred
- Grades 3 and 4 decrease in white blood cell count
- Grade 3 decrease in neutrophil count
- Grade 4 decrease in neutrophil count lasting ≤ 7 days
- Grades 3 and 4 decrease in lymphocyte count

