7.7 Pazopanib Dose Modification Instructions

In addition to the general dose modification instructions provided in Section 7.4, dose modification instructions for pazopanib-related toxicities are listed in Table 7, Table 8 (liver function abnormalities), Table 9 (PPE), and Table 10 (Other).

Note: For some toxicities, AR-42 instructions are also included on the tables listed above.

Toxicity	Pazopanib Modification			
	(Refer to Table 6 for pazopanib dose reduction steps)			
Cardiac	Hold/omit ^A pazopanib and determine LVEF.			
Grade 2 heart failure	 If < 15% absolute decline in LVEF compared with baseline or a decline in LVEF of < 10% compared with baseline and ≥ 50%: When symptoms of heart failure show clinical improvement, resume pazopanib with reduction in dose of one dose reduction step.^B If ≥ 15% absolute decline in LVEF compared with baseline or a decline in LVEF of ≥ 10% compared with baseline and < 50%: Continue holding until clinical improvement in symptoms and until LVEF improves to within 10% of baseline. Refer patient for cardiology consult. Reduce pazopanib dose by one dose reduction step when resuming treatment.^B At investigator's discretion, pazopanib may be discontinued. 			
Grade 3 or 4 heart failure	Discontinue pazopanib (also discontinue AR-42).			
Grade 3 or 4 MI	Discontinue pazopanib (also discontinue AR-42).			
Endocrine Disorders				
Grade 2 hypothyroidism	Continue pazopanib (dose reduction not required); initiate hypothyroidism management.			
Grade 3 or 4 hypothyroidism	Discontinue pazopanib; initiate/continue hypothyroidism management.			
Gastrointestinal Disorders				
≥ Grade 1 fistula	Discontinue pazopanib (also discontinue AR-42).			
≥ Grade 2 perforation				
Investigations				

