	 calcium abnormalities are corrected, symptoms resolved, and QTc improved to ≤ grade 1 (≤ 480ms). Reintroduce pazopanib and AR-42 with input from cardiology and with additional QTc evaluation, either concurrent with reintroduction or at earliest possible opportunity within 8 days from reintroduction. If event is thought to be related to study treatment, reduce the dose of pazopanib and AR-42 by one dose reduction step when resuming study treatment.^B Consider chronic supplementation for maintenance of electrolytes. For recurrent syncope or near-syncope thought to be related to study treatment, consider discontinuation of both pazopanib and AR-42.
Renal and Urinary Disorders	
≥ Grade 2 proteinuria	 Hold/omit^A pazopanib. If assessment of proteinuria was based on a urine dipstick reading, a 24-hour urine collection is required. Based on the 24-hour urine specimen: If grade 2 proteinuria, consult nephrology. If urine protein is < 3.0 gm/24 hours, study treatment may be continued without dose modification pending nephrology consult. If ≥ 3.0 gm/24 hours, hold study treatment until improvement to < 3.0 gm/24 hours or additional nephrology recommendations. If grade 3 proteinuria, consult nephrology and discontinue pazopanib.
Respiratory, Thoracic, and M	ediastinal Disorders
≥ Grade 2 pneumonitis	Discontinue pazopanib (also discontinue AR-42).
Skin and Subcutaneous Disc	rders
PPE (hand-foot syndrome)	See Table 9 for instructions related to PPE

Table 7. Pazopanib Dose Modification Instructions (continued)

Table 7. Pazopanib Dose Modification Instructions (continued)

Tuble III azopanie Beee mea	
Vascular Disorders	
Grade 3 hypertension defined as systolic BP >160 mmHg and diastolic BP >100 mm/Hg	 Hold/omit^A pazopanib until resolution to ≤ grade 2. Administer standard antihypertensive therapy. When resuming pazopanib, decrease pazopanib dose by one dose reduction step; monitor BP weekly for 4 weeks. If BP remains controlled for at least one cycle, the pazopanib dose may be escalated by one dose step at the investigator's discretion.
Grade 4 hypertension	Discontinue pazopanib (also discontinue AR-42)
	an the first 4 weeks of the cycle, any remaining doses for that cycle are 7.4 for additional information.

B. At the investigator's discretion (after the DLT evaluation period [Section 6.7.1]), the dose may be escalated by one dose step when the toxicity has resolved and treatment can be resumed.

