7.7.1 Liver Function Abnormalities

For patients with observed worsening of serum liver tests considered to be related to pazopanib (ie, where no alternative cause is evident, such as post-hepatic cholestasis or disease progression), the dose modification and monitoring instructions in the table below will be followed.

Increase in AST/ALT (per NCI CTCAE v4.0)	First Occurrence	Restart	Recurrence	
Grade 2 ALT and/or AST > 3-5 x ULN	Continue study treatment with weekly monitoring of liver function until transaminases return to grade 1 or baseline.			
Grade 3 ALT and/or AST > 5-20 x ULN	Hold/omit pazopanib and AR-42; weekly monitoring until transaminases return to grade 1 or baseline. ^A	If the potential benefit of reinitiating study treatment is considered to outweigh the risk of hepatotoxicity, reduce pazopanib and AR-42 by one dose reduction step. ^B	Discontinue pazopanib and AR-42	
	grade for baseline.	Measure serum transaminases weekly for at least 4 weeks.		
Grade 2 or 3 with Concurrent Bilirubin Elevation ALT and/or AST > 3-20 x ULN and Bilirubin > 2 x ULN	Hold/omit pazopanib and AR-42; weekly monitoring until transaminases return to grade 1 or baseline. ^A If the potential benefit of reinitiating study treatment is considered to outweigh the risk of hepatotoxicity, reduce pazopanib and AR-42 by one dose reduction step. ^B Measure serum transaminases and bilirubin weekly for at least 4 weeks .		Discontinue pazopanib and AR-42	
Grade 4 ALT and/or AST > 20 x ULN	ALT and/or AST Discontinue pazopanib and AR-42.			
 A. If more than a 3-week delay is required, discontinue pazopanib. B. Refer to Table 6 for pazopanib dose reduction steps. 				

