7.7.2 PPE

Refer to Section 6.9.4 for supportive care instructions and recommendations for the prevention and treatment of PPE. Refer to the table below for study treatment instructions.

Grade of event (NCI CTCAE v4.0)	Occurrence	Pazopanib Dose Modification ^A (Refer to Table 6 for pazopanib dose reduction steps.)
 Grade 1 Minimal skin changes or dermatitis (eg, erythema, edema, hyperkeratosis) without pain Numbness, dysesthesia, paresthesia, tingling, painless swelling, or erythema of hands and/or feet Does not disrupt normal activities 	Any	Continue study treatment; maintain dose level.
 Grade 2 Skin changes (eg, peeling, blisters, bleeding, edema, or hyperkeratosis) with pain Painful erythema and swelling of hands and/or feet Limiting instrumental ADL^B 	Any	 If PPE is NOT interfering with instrumental ADL, maintain pazopanib (and AR-42) dose. If PPE is interfering with instrumental ADL, reduce pazopanib by one dose reduction step for the remainder of the treatment cycle.^C If no improvement in spite of supportive care and pazopanib dose reduction, omit pazopanib for the remainder of the cycle. When resuming treatment, decrease pazopanib dose by one dose reduction step.^{C,D}
Grade 3 • Severe skin changes (eg, peeling, blisters, bleeding, edema, or	1 st Occurrence	 Omit pazopanib and AR-42 for a minimum of 7 days and until toxicity resolves to ≤ grade 1.^D When resuming treatment, decrease pazopanib dose by one dose reduction step.^C
 hyperkeratosis) with pain Moist desquamation, ulceration, blistering, or severe pain of the hands and/or feet 	2 nd Occurrence	 Omit pazopanib and AR-42 for a minimum of 7 days and until toxicity resolves to ≤ grade 1.^D When resuming treatment, decrease pazopanib dose by one dose reduction step.^C
Limiting self-care ADL ^E	3 rd Occurrence	Discontinue pazopanib and AR-42.

Table 9	Pazonanih	Dose	Modification	Instructions for	r PPF
Table 5.		0030	mounication	monuono ic	

A. More conservative management is permitted per investigator discretion.

B. Instrumental ADL refer to preparing meals, shopping for groceries or clothes, using the telephone managing money, etc.

C. If toxicity returns to ≤ grade 1 after dose reduction, pazopanib escalation is permitted, **up to the enrolled dose level**, at the discretion of the investigator if the patient has completed 1 cycle at a reduced dose without recurrence of the event.

D. If > 3 consecutive weeks of delay are required for recovery, discontinue pazopanib and AR-42.

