13.6 Evaluability for DLT, Toxicity, and Response

13.6.1 DLT-Evaluable Population

DLT-evaluable patients are those who have taken a minimum of 6 doses of AR-42 during the first treatment cycle and a minimum of 21 doses of pazopanib during the first treatment cycle, or those who have experienced a DLT with any study treatment during cycle 1 as described in Section 6.7.1.

Note: Patients who for any reason are not evaluable for DLT will be replaced.

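### A non-DLT patient short of cycle-1 doses is replaced even when study-drug toxicity caused the shortfall, and the classification can turn on a single day

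*Combined protocol and SAP*

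**What the plan says.** Section 6.7.1 sets the exposure minimum for a patient without a DLT: "Patients must have taken a minimum of 6 AR-42 doses", together with at least 21 pazopanib doses, in cycle 1. Section 13.6.1 repeats this and adds: "Note: Patients who for any reason are not evaluable for DLT will be replaced". Neither section separates shortfalls by cause.

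Section 6.7.2 defines DLT by grade (3 or higher), attribution and a list of exemptions. One exemption is "The first incidence of grade 3 PPE at any dose level". A hold or permanent stop for toxicity is not in itself a DLT.

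Section 7 then stops or holds both drugs for events that can fall outside that definition:

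- Table 7 discontinues both drugs for "≥ Grade 1 fistula", for perforation and RPLS from grade 2, and for "≥ Grade 2 pneumonitis".
- Table 9, for a first grade 3 PPE: "Omit pazopanib and AR-42 for a minimum of 7 days and until toxicity resolves to" grade 1 or lower.
- Table 8, for grade 2 or 3 ALT/AST with bilirubin above 2 x ULN: "Hold/omit pazopanib and AR-42; weekly monitoring until transaminases return to grade 1 or baseline".

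Sections 6.2.1 and 7.4 allow an interrupted cycle to run to 5 weeks but do not require it. Table 3 makes the escalation decision and requires at least 6 DLT-evaluable patients before a level is accepted as not exceeding the MTD.

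**The concern.** Replacing a patient is harmless when the reason has nothing to do with the drug. Here the drug can be the reason: an attributed toxicity stops or holds treatment, the patient misses the dose minimum, and the count that decides escalation and the MTD no longer contains that patient. The exclusion is informative.

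The classification is also unstable. The same toxicity can lead to replacement or to a DLT-free count depending on its onset day, on one more day of omission, or on whether the site chose to extend the cycle. Neither result records that toxicity interrupted or ended treatment, and two investigators following the protocol could classify the same patient differently.

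**Working it through.** **The plan's own figure.** Section 13.2 allows for up to 20% inevaluable patients: 36/(1 − 0.20) = 45, and 45 + 6 = 51. Both reproduce and neither is in dispute. The 20% is not split by cause.

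**Dose margins** (Sections 6.2 and 6.7.1). AR-42: 9 planned, 6 needed, so at most 3 may be missed. Pazopanib: 28 planned, 21 needed, so at most 7 may be missed; in a 35-day cycle, 35 − 21 = 14.

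**Permanent stop of both drugs on day s.** Pazopanib doses taken = s − 1.

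| Stop on | Pazopanib doses | Result if no DLT |
|---|---|---|
| day 21 | 20 | replaced |
| day 22 | 21 (with all 9 AR-42) | counted DLT-free |

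This applies to the Table 7 stops when the event is below grade 3.

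**Temporary omission of both drugs.** I took AR-42 on days 1, 3, 5, 8, 10, 12, 15, 17 and 19, pazopanib daily, and tried every start day.

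| Cycle | Days omitted | Pazopanib doses | Result if no DLT |
|---|---|---|---|
| 28 days | 7, any start | at least 21 (AR-42 at least 6) | counted DLT-free |
| 28 days | 8, starting by day 21 | 28 − 8 = 20 | replaced |
| 35 days | 14 | 35 − 14 = 21 | pazopanib minimum met |
| 35 days | 15 | 35 − 15 = 20 | replaced |

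The shortest PPE omission in Table 9 (7 days) therefore sits exactly on the evaluability limit. For Table 8, if the first weekly recheck does not allow a restart, the hold passes 7 days. That path exists only if the bilirubin rise is also below grade 3, and the documents do not give that cut-off.

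**Effect on the escalation decision.** Inputs: d = probability of a DLT in cycle 1; q = probability of a non-DLT toxicity that leaves too few doses. The documents give neither, so both are assumptions. Patients are taken as independent. Under Table 3 a level passes with 0 of 3, or with 1 of 3 followed by 0 of 3:

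P(r) = (1 − r)³ + 3r(1 − r)² × (1 − r)³

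The DLT rate r entering Table 3 is d/(1 − q) with replacement, d + q if all such patients are events, and d if all are DLT-free.

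For d = 0.20 and all DLT-free: 0.512 + 0.197 = 0.709. For the others:

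| q | Replaced: r, P | All events: r, P | Difference |
|---|---|---|---|
| 1% | 0.2020, 0.704 | 0.21, 0.687 | 0.017 |
| 2% | 0.2041, 0.700 | 0.22, 0.665 | 0.035 |
| 5% | 0.2105, 0.686 | 0.25, 0.600 | 0.086 |

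At q = 2% the difference is 0.031, 0.035, 0.035, 0.032 and 0.028 for d = 10%, 15%, 20%, 25% and 30%, so it hardly depends on d.

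**What the documents say about q.** The nearest figure is 2% grade 3 skin disorder in STS (Table 16; nearly all skin disorder was PPE). It is for pazopanib alone over all treatment, not cycle 1 of the combination, and only omissions beyond the limit would count. Fistula, perforation, RPLS and pneumonitis are not in Tables 13 to 18. The 5% row is assumption only.

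**The case against.** **Direction.** A reader might infer that replacement hides toxicity and pushes the MTD upward. The documents do not support that. Replacement gives d/(1 − q), which is above d, so passing a level is slightly harder than if these patients were counted under Section 6.7.2 as it stands (0.700 against 0.709 at q = 2%). A loss of caution appears only against a rule that counts every such patient as an event, and Section 6.7.2 excludes these events by grade or by name. This stands.

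**Size.** A reader might also take the 20% in Section 13.2 as q and find a large effect. That figure is a ceiling for inevaluability from all causes, not from toxicity. Most attributed events of grade 3 or higher are DLTs and stay in the count. This stands too.

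**Conditions on two paths.** Section 6.7.2 does not say whether the first grade 3 PPE means first per patient or first in the study. On the second reading at most one patient is affected. The Table 8 path needs the bilirubin condition above. The Table 7 path needs neither.

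**Existing safeguards.** Section 6.7.4 lets the RP2D be set below the MTD in view of non-DLT events and dose modifications. Section 13.3 lists dose modification and DLT evaluability. Section 13.6.2 keeps replaced patients in the safety analysis, and Section 7.1 records interruptions. These soften the problem, but 6.7.4 is discretionary, 13.3 does not ask for the cause, and none of them changes the Table 3 count.

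**Boundaries.** Any minimum-dose rule has one. True, but a boundary matters less when the event that crosses it is unrelated to the drug.

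**Conclusion.** The point holds as a minor one. The stated rules let attributed toxicity remove a patient from the escalation count, and they classify the same event differently according to timing and an optional extension. That follows from the text and the dose counts, whatever q is.

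The numerical effect is probably small: a difference in pass probability of about 0.02 to 0.035 at q = 1% to 2%, and only if every such patient would otherwise be an event. It rests on an assumed d and q. The planned sample size is unaffected.

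**What to change.** 1. In 6.7.1 and 13.6.1, limit replacement to shortfalls not caused by study-drug toxicity, and keep toxicity-caused shortfalls in the Table 3 count.
2. Reconcile 6.7.2 with the stop and hold rules in Tables 5 and 7 to 9, so that each non-DLT stop or hold has one pre-specified classification, event or DLT-free. Which of the two is the sponsor's decision. It should not change with onset day, length of hold or cycle extension. Say also whether the PPE exemption is per patient or for the whole study.
3. State whether doses in an extended cycle, and doses below the assigned level, count toward 6 and 21. The second arises, for example, under Table 9 for grade 2 PPE that limits instrumental ADL: "reduce pazopanib by one dose reduction step for the remainder of the treatment cycle".
4. In 13.3, list non-evaluable patients and non-DLT cycle-1 stops and holds by cause and dose level.

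The cost is wording and one listing, mostly from data already collected. For toxicities classified as events, escalation becomes somewhat more conservative (0.704 to 0.687 at q = 1%, 0.700 to 0.665 at q = 2%, with d = 20%). For those classified DLT-free it becomes slightly less conservative than now (0.700 to 0.709 at q = 2%).

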13.6.2 Safety-Evaluable Population

Patients who have received any study treatment will be evaluable for safety and toxicity analyses.

13.6.3 Efficacy-Evaluable Population

Efficacy-evaluable patients are those who have received any doses of AR-42 and pazopanib in cycle 2 (regardless of the number of doses taken during cycle 1), and have had at least 1 imaging assessment of response after receiving study treatment.

For efficacy evaluation, patients are coded as having a response or not having a response as follows:

- Responders: Best response assessment is a PR or a CR (Section 10).
- Non-Responders: Best response assessment is stable disease or progressive disease; also included are patients who did not have assessment of tumor response at least once after initiation of study treatment or who were otherwise not evaluable for response.

The coding of patients as responders or non-responders will be made by the Sponsor-Investigator with the concurrence of the Biostatistician.

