7.4 General Instructions and Guidelines

- If treatment delays are required, the cycle may be extended to 5 weeks; however, all AR-42 doses must be taken during the first 4 weeks of the 5-week cycle. Any doses not given within the first 4 weeks of the extended cycle will be omitted.
- If one or both of the study medications are held due to toxicity, a **maximum of 3 consecutive weeks is permitted for recovery**. If recovery has not been sufficient to resume treatment 3 consecutive weeks after the decision to hold either or both of the study medications, both study medications must be discontinued.
- If AR-42 treatment must be interrupted for an AR-42-related toxicity, the patient should continue taking pazopanib unless dose modification instructions specifically indicate that pazopanib should be held or omitted.
- If pazopanib treatment must be interrupted due to a pazopanib-related toxicity, the patient should continue taking AR-42 unless dose modification instructions specifically indicate that AR-42 should be held or omitted..

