10.2 Imaging

Only imaging of the initial sites of disease is required at subsequent time points to provide tumor measurements for assessment of antitumor effect. Brain imaging after initiation of study therapy is only required for patients who have a history of brain metastasis.

The same type of imaging used at baseline should be used at each scheduled assessment which will be performed at the end of every other 4-week cycle (ie, approximately every 8 weeks). At the investigator's discretion, additional imaging may be performed when clinically indicated.

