13.4 Statistical Analysis for Secondary Objectives

Patients' demographics, AEs and SAEs, treatment status, number of patients who had discontinuation of study therapy, and clinical response will be listed and summary descriptive statistics, including frequency/proportion for discrete variables and mean/median/standard deviation for continuous variables, will be calculated. The clinical response (CR + PR) rate will also be calculated along with its 95% confidence interval.

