13.5 Statistical Analysis for Exploratory Objectives

The study is not sufficiently powered to establish definitive outcomes for the correlative exploratory endpoint. Any comparison with a significant alpha, 0.05, will be deemed of interest to warrant further evaluation. An ordinal regression and a logistic regression will be used to assess the association between expression of each biomarker and clinical response.

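### The CR + PR rate has no fixed denominator: Section 13.6.3 codes as non-responders patients whom its own efficacy set excludes, and Section 13.4 names no population

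*Combined protocol and SAP*

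**What the plan says.** Section 13.6.3 sets two conditions for the efficacy set. The first is dosing: "Efficacy-evaluable patients are those who have received any doses of AR-42 and pazopanib in cycle 2". The second is imaging: "and have had at least 1 imaging assessment of response after receiving study treatment".

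Under the same heading, the section then sorts patients into responders and non-responders. Besides stable and progressive disease, the non-responder group takes in the unassessed: "also included are patients who did not have assessment of tumor response at least once after initiation of study treatment". It also takes in patients who could not be evaluated for other reasons.

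Section 13.4 specifies the estimate but not the population: "The clinical response (CR + PR) rate will also be calculated along with its 95% confidence interval". Section 13.6.2 defines an any-treatment population but gives it only to safety: "Patients who have received any study treatment will be evaluable for safety and toxicity analyses".

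Section 13.5 uses response again as an outcome, also without naming a population: "An ordinal regression and a logistic regression will be used to assess the association between expression of each biomarker and clinical response".

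**The concern.** A patient with no post-treatment assessment fails the imaging condition and so lies outside the efficacy set. If that set is the denominator, the rule for unassessed patients applies to nobody. If the rule is to have any effect, the denominator must be wider than the set. Both readings have support in the text.

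The choice matters because leaving the narrow set can depend on outcome. Early progression, death or toxicity can stop a patient before any cycle-2 dose or before the first scheduled scan. Removing such patients usually raises the rate. The CR + PR rate is the only efficacy estimate for which the plan asks for a confidence interval, and in an open-label trial its denominator could be settled with the results known. The regressions in Section 13.5 inherit the same ambiguity.

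**Working it through.** **Who moves in or out.** Section 10.2 schedules imaging at the end of every other cycle, and Table 20 puts the first scheduled assessment at about day 1 of cycle 3. Earlier scans are optional: "additional imaging may be performed when clinically indicated". Table 20 asks for a final scan only in patients who stop without progression and were last assessed 8 or more weeks before, and then only where possible. Taking the two rules in Section 13.6.3 in turn:

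| Patient | In the efficacy set? | Coded by the response rule |
|---|---|---|
| Stops in cycle 1, never imaged | No (fails both conditions) | Non-responder |
| Progresses on an early scan, no cycle 2 | No (fails dosing) | Non-responder |
| Both drugs in cycle 2, never imaged | No (fails imaging) | Non-responder |
| Both drugs in cycle 2, early extra scan | Yes | By best response |

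The first three rows are the conflict. The third row also allows a further reading, in which everyone dosed in cycle 2 is counted, with or without an image.

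**Range of N (Section 13.2).** The plan's sample size reproduces.
- Maximum: 36 / (1 − 0.20) = 45; 45 + 6 = 51.
- Likely, low end: 4 × 4.5 = 18; 18 / 0.8 = 22.5, rounded up to 23; 23 + 6 = 29.
- Likely, high end: 5 × 4.5 = 22.5, rounded up to 23; 23 / 0.8 = 28.75, rounded up to 29; 29 + 6 = 35.

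The 20% in that section concerns DLT evaluability. It is not an exclusion rate for response.

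**Size of the effect.** The documents give neither an expected number of responders nor an exclusion rate, so the counts below are assumptions. Section 13.4 names no interval method; I use exact (Clopper-Pearson) intervals. If x of N treated patients are excluded and none of them responded, the rate is multiplied by N / (N − x). Take N = 32, the midpoint of 29 and 35, with 6 responders:

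| Denominator | Rate | Exact 95% CI | Factor |
|---|---|---|---|
| All treated, 6/32 | 18.8% | 7.2 to 36.4 | 1 |
| 3 non-responders excluded, 6/29 | 20.7% | 8.0 to 39.7 | 32/29 = 1.10 |
| 6 non-responders excluded, 6/26 | 23.1% | 9.0 to 43.6 | 32/26 = 1.23 |
| 6 excluded, 1 a responder, 5/26 | 19.2% | 6.6 to 39.4 | – |
| 6 excluded, 2 responders, 4/26 | 15.4% | 4.4 to 34.9 | – |

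Across the likely range of N, the factor runs from 29/26 = 1.12 to 35/32 = 1.09 for x = 3, and from 29/23 = 1.26 to 35/29 = 1.21 for x = 6.

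**Second set of assumptions.** With 5 responders and roughly 10%, 20% or 30% excluded:
- N = 29: 5/29 = 17.2% becomes 5/26 = 19.2%, 5/23 = 21.7% or 5/20 = 25.0%.
- N = 35: 5/35 = 14.3% becomes 5/31 = 16.1%, 5/28 = 17.9% or 5/25 = 20.0%.

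**The case against.** The best reply is that Section 13.6 is where the plan assigns populations, and 13.6.3 is its entry for efficacy. Section 13.4 names no population for adverse events either, yet nobody doubts that 13.6.2 governs them. On this view the only fault is one stray clause. That is a fair account of the layout, but it leaves an explicit coding rule with nobody to apply to, and it settles on a denominator that depends on what happened after treatment began. Nothing elsewhere reconciles the two sentences.

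Section 13.4 also requires treatment status, discontinuations and response to be listed, so a reader of the listings could compute either rate. Section 13.6.3 requires the biostatistician to concur with the coding. Both help, but neither fixes which rate is reported.

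The excluded-responder case is narrow. Section 7.4 says "If AR-42 treatment must be interrupted for an AR-42-related toxicity, the patient should continue taking pazopanib", unless other instructions say otherwise, but it also caps a toxicity hold at 3 consecutive weeks. AR-42 is taken only in weeks 1 to 3 of a standard cycle, so missing every cycle-2 dose through a hold means a hold close to that cap. Section 10.3 further requires a response to be confirmed at least 4 weeks later. The case is therefore unlikely but possible. It is a reason not to call the upward bias certain.

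The point about weight stands. The rate is descriptive, with no target or decision rule. It pools RCC and STS, for which the protocol cites partial-response figures of 31% and 6% on pazopanib (Sections 1.2.1 and 1.2.2). The shifts shown are small beside intervals 29 to 35 points wide.

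**Conclusion.** The concern holds. It is a contradiction between two stated rules in Section 13.6.3, left open by Section 13.4, and it should be fixed before analysis. If 3 to 6 excluded patients are all non-responders, the narrow reading multiplies the rate by 1.09 to 1.26 over the likely N of 29 to 35. Those exclusion counts are assumed. The upward direction is expected but not guaranteed, since it requires the excluded patients to respond less often than those kept. The primary objective, the safety analyses and the sample size are unaffected.

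**What to change.** - **Sections 13.4 and 13.6.3:** name all patients who received any study treatment (the Section 13.6.2 population) as the primary denominator for the CR + PR rate and its interval. Count unassessed and otherwise non-evaluable patients as non-responders, as the existing bullet already does.
- **Sensitivity analysis:** keep the cycle-2 dosing and imaging set, label the result as such, and report how many patients were excluded and why.
- **Section 13.5:** use the same population and coding in the logistic regression, necessarily limited to treated patients with archived tissue, because Section 11.1 requires tissue only where it exists. State the category that unassessed patients take in the ordinal regression.

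The cost is wording in three sections, with no new data or patients. Making all treated patients primary goes a step beyond removing the contradiction, but it is the reading under which the existing non-responder rule has effect. The reported rate will probably be slightly less favourable than under the narrow set.
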